6.7.6. Pediatric Anxiety Rating Scale – Revised (PARS-R)

The PARS-R will be completed at Screening, Weeks 14, 22, 30, and Week 38. The patient must have a severity score of 10 or higher at Screening and Visit 2 in order to be eligible for participation.

The PARS-R is a clinician-rated caregiver interview that covers 61 behaviors related to anxiety (Riddle, Ginsburg, Palapattu, & Walkup 2004, Riddle et al. 2002). The PARS-R provides broad coverage of separation anxiety, social phobia, and generalized anxiety. Symptoms are further categorized into Social Interactions or Performance Situations, Separation, Generalized, Specific Phobia, Panic Symptoms/Physical Signs, Obsessive-Compulsive, Health/Illness Concerns, and Other. The interviewer assesses the severity by quantifying the frequency and degree of interference and avoidance in family, school and community settings. Each of seven severity items is scored on a scale of 1 to 5, with 5 being the most severe and frequent. The final score is

the sum of five of the seven severity items. The five-item scale is recommended for use during treatment studies ([Riddle et al. 2004](#), [Riddle et al. 2002](#)). Studies show excellent inter-rater reliability (even across sites kappa .87-.90) and test retest reliability after 3 to 8 weeks in 49 individuals with FXS ages 5 to 35 years of age ([Russo- Ponsaran et al. 2014 AJIDD](#)).

6.7.7. Anxiety, Depression, and Mood Scale (ADAMS)

The Anxiety, Depression, and Mood Scale will be completed by the parent/caregiver, with support from the site staff, at Screening, Visit 2, Visit 3, Visit 4, Visit 5, Visit 6, and Visit 7 EOS/ET. The ADAMS will be used as a comprehensive assessment of anxiety, depression, and mood among the FXS patients. The ADAMS is comprised of 28 items, which are rated on a scale of “0 - not a problem” to “3 - severe problem.” The ADAMS yields a total score as well as five subscale scores: “Manic/Hyperactive Behavior,” “Depressed Mood,” “Social Avoidance,” “General Anxiety,” and “Compulsive Behavior.” The ADAMS has been validated and has demonstrated good internal consistency and test-retest reliability. Interrater reliability has been shown to be satisfactory ([Esbensen et al. 2003](#)).

7. PHARMACOKINETIC ANALYSES

7.1.1. PK Sample for Determination of CBD/THC

The following PK parameters for determination of CBD/THC will be calculated/derived from the data. Plasma PK will be calculated on:

Trough: Steady-state plasma concentration occurring just prior to the next dose of ZYN002.

Elapsed time between the last ZYN002 dose and time of plasma sample collection.

Descriptive statistics (arithmetic mean, median, SD, minimum, maximum, coefficient of variation, geometric mean [plasma concentration]) for the plasma trough concentrations and elapsed time will be presented at each nominal blood sampling time (Screening, pre-dose Week 6, 14, and Week 38 EOS/ET. Analyses for CBD metabolites are exploratory and may be conducted.

7.1.2. PK Sample Determination of AED Medications

The following data will be summarized separately for each AED medication:

- Plasma concentration occurring at Screening, pre-dose Week 6, 14, and Week 38 EOS/ET.
- Elapsed time between last AED dose and the time of plasma sample collection.

Descriptive statistics (arithmetic mean, median, SD, minimum, maximum, coefficient of variation, geometric mean [plasma concentration]) for the AED plasma trough concentrations and elapse time will be presented at each nominal PK sampling time.

8. SAFETY ANALYSES

The safety analysis set will be used for all safety analyses. Study drug administration, AEs and concomitant medications will be summarized by treatment period (Period 1, 2, and overall).

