4. STUDY DESIGN

This is an open-label study to assess the safety, tolerability and efficacy of CBD administered as ZYN002, a transdermal gel, for the treatment of child and adolescent patients with 22q. Male and female patients with 22q will be treated in Period 1 for 14 weeks.

Patients with less than a 25% improvement from baseline in the ABC-C Irritability subscale may have their total dose increased by the investigator at Week 6.

Patients that have made a $\geq 35\%$ improvement on the ABC-C Irritability sub-scale will be allowed to continue to Period 2 for an additional 24 weeks of treatment. Only patients taking AED medications for treatment of seizures or epilepsy will have an additional one or two-week Taper Period.

Approximately 20 male and female patients, ages 4 to < 18 years, will receive ZYN002.

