5.2. Data included in Period 1 Analyses

The records to be included in the Period 1 analyses will include all records with a nominal visit of ≤ 4 (Week 14/ET). All summaries will include one column only identified as ZYN002.

In an attempt to include all Period 1 Concomitant Medications and Adverse Events in the Period 1 analyses TGG will need to calculate a Week 14 Date for both subjects who completed Period 1 and who discontinued in Period 1 before Week 14. This will be accomplished by the following steps using the last non-missing value as the actual or imputed Week 14 date:

- a) If a subject completes Period 1 then use their actual Week 14 Date.
- b) If a subject discontinues before Week 14 date and their last nominal visit is identified as Week 14/ET then add ‘X’ days to that date to get to Day 98 (7 times 14).
- c) If Week 6, TGG will impute the Week 14 cutoff date to be the Week 6 date plus (7 times 8) to get the Week 14 imputed Date

d) If Day 1, TGG will impute the Week 14 date to be Day 1 plus (7 times 14)

Treatment emergent adverse events and concomitant medication summaries will include start dates that occur any time before treatment begins and treatment ends. Refer to [Section 6.2.3](#).

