6.2.4. Treatment Emergent Adverse Events (TEAEs)

Treatment emergent adverse events (denoted as TEAE hereafter) are defined as adverse events with onset dates on or after the start of study drug.

All reports of adverse events should include the severity and relationship to study drug that are determined by the investigators. In the event of missing information, the following rules will be applied for the adverse event summaries:

- AEs with missing onset dates will be included as treatment- emergent (unless end date is prior to the first dose date)
- AEs with missing severity will be counted as severe in severity
- AEs with missing relationship to study drug will be counted as related

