6.4. Analysis Populations

6.4.1. Safety Analysis Set

All patients who receive at least one dose of study drug will be included in the safety population. Safety population will be used for all safety evaluations.

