8.1.1. Adverse Events

All adverse events will be coded using the Medical Dictionary for Regulatory Activities (MedDRA) Version 21.0 or greater. Treatment emergent adverse events (TEAEs) are defined as adverse events with onset dates on or after the first dose of study drug.

All AE summaries will include total number of TEAEs and total number of patients with AEs.

An overall summary of adverse events will include number (%) of patients reporting ≥ 1 TEAE (and number of TEAEs), TEAE by Severity (and number of TEAEs), treatment-related TEAEs (and number of TEAEs), SAEs (and number of TEAEs), TEAE by outcome (and number of TEAEs), TEAEs that resulted in treatment discontinuation (and number of TEAEs). In addition, the total number of TEAEs by subject will be summarized.

Additionally, summaries will be presented for all TEAEs by system organ class and preferred term (overall and by severity). TEAEs determined by the investigator to be treatment-related (overall and by severity). Serious AEs will also be summarized. Adverse events causing permanent discontinuation from treatment will be summarized, fatal adverse events will be summarized, and TEAEs by preferred term in descending order will be summarized.

The incidence of adverse events will be summarized using descriptive statistics by system organ class and preferred term. Patients are counted only once in each system organ class category, and only once in each preferred term category. Treatment-related adverse event summaries will include adverse events with missing relationship to study drug. For the summaries by severity, patients and TEAEs are counted at the greatest severity.

AEs will be summarized separately for each treatment Period (1, 2) and overall (the whole study).

Listings for fatal AEs, serious AEs, and AEs leading to discontinuation, will also be presented.

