11. LIST OF SUMMARIES AND LISTINGS

Summary Number	Title	Population	Period 1 Display
14.1.1	Summary of Patient Disposition	Enrolled	X
14.1.2	Summary of Demographics	Safety Analysis Set	X
14.1.3	Summary of Baseline Characteristics	Safety Analysis Set	X
14.1.4	Summary of Medical History	Safety Analysis Set	X
14.1.5	Summary of Prior Medications by Therapeutic Class and Preferred Term	Safety Analysis Set	X
14.1.6	Summary of Electrocardiogram Findings at Baseline	Safety Analysis Set	X
14.1.7	Summary of Physical Examination Findings at Baseline	Safety Analysis Set	X
14.1.8	Summary of Neurological Examination Findings at Baseline	Safety Analysis Set	X
14.2.1	Summary of Change from Baseline to Weeks 6, 14, 22, 30, and 38 in the ABC-C Checklist	mITT Analysis Set	X
14.2.2	Summary of 25% and 50% responders at Weeks 6, 14, 22, 30, and 38 in the ABC-C Checklist	mITT Analysis Set	X
14.2.3	Summary of Change from Baseline to Weeks 6, 14, 22, 30, and 38 in the ADAMS Checklist	mITT Analysis Set	X
14.2.4	Summary of Change from Baseline to Weeks 6, 14, 22, 30, and 38 in the CGI-S Scale	mITT Analysis Set	X
14.2.5.1	Summary of CGI-I at Baseline, Weeks 6, 14, 22, 30, and 38	mITT Analysis Set	X
14.2.5.2	Shifts from Baseline to Weeks 6, 14, 22, 30, and 38 in CGI-I	mITT Analysis Set	X
14.2.6.1	Summary of Change from Baseline to Weeks 6, 14, 22, 30, and 38 in the PARs-R Scale	mITT Analysis Set	X
14.2.6.2	Summary of Shifts from Baseline to Weeks 6, 14, 22, 30, and 38 in CGI –I Categories (≤ 52 and > 52)	mITT Analysis Set	X
14.3.1.1.1	Summary of Sachet Information (Period 1)	Safety Analysis Set	X
14.3.1.1.2	Summary of Study Drug Duration (Period 1)	Safety Analysis Set	X
14.3.1.2.1	Summary of Sachet Information (Period 2)	Safety Analysis Set	
14.3.1.2.2	Summary of Study Drug Duration (Period 2)	Safety Analysis Set	
14.3.1.3.1	Summary of Sachet Information (Overall)	Safety Analysis Set	
14.3.1.3.2	Summary of Study Drug Duration (Overall)	Safety Analysis Set	
14.3.2.1.1	Overall Summary of Treatment Emergent Adverse Events (Period 1)	Safety Analysis Set	X
14.3.2.1.2	Overall Summary of Treatment Emergent Adverse Events (Period 2)	Safety Analysis Set	
14.3.2.1.3	Overall Summary of Treatment Emergent Adverse Events (Overall)	Safety Analysis Set	
14.3.2.2.1	Summary of Treatment Emergent Adverse Events by System Organ Class, and Preferred Term (Period 1)	Safety Analysis Set	X

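### The Period 2 adverse-event tables are assigned everyone ever dosed as their population, so Period 2 percentages would be understated by the ratio of patients dosed to patients who entered the extension.

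*SAP*

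**What the plan says.** SAP Section 8 asks for study drug administration, adverse events and concomitant medications by Period 1, Period 2 and overall, and fixes the population: "The safety analysis set will be used for all safety analyses". Section 6.4.1 defines that population: "All patients who receive at least one dose of study drug will be included in the safety population". Sections 6.4 and 6.5 define safety, mITT and pharmacokinetic sets, and nothing specific to Period 2.

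Section 11 lists 12 Period 2 tables. Two cover exposure (14.3.1.2.1 and 14.3.1.2.2). Ten cover adverse events (14.3.2.1.2 to 14.3.2.9.2), including the serious, fatal and discontinuation tables. All carry the Safety Analysis Set label. Section 8.1.7 also wants concomitant medications by period, although Section 11 lists a single table (14.3.7) with no period split.

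Entry to Period 2 is restricted. In SAP Section 4, patients with at least 35% improvement on ABC-C irritability "will be allowed to continue to Period 2 for an additional 24 weeks of treatment". On study size: "Approximately 20 male and female patients, ages 4 to < 18 years, will receive ZYN002". The number entering the extension is to be reported in the disposition summary (Section 6.3.1).

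On the treatment-emergent window, Section 6.2.4 says such events "are defined as adverse events with onset dates on or after the start of study drug", and Section 8.1.1 repeats the rule from first dose. Section 5.2, on the Period 1 analyses, says that treatment-emergent event and concomitant-medication "summaries will include start dates that occur any time before treatment begins and treatment ends", and refers the reader to Section 6.2.3.

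The Note to File at the front of the SAP says data were collected as a single arm rather than by dose or by period, and that the protocol and SAP will not be updated.

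**The concern.** A patient who leaves at Week 14 cannot have an event on extension treatment. If that patient stays in the denominator of a Period 2 table, the table reports absence of exposure as absence of harm. The primary objective is safety and tolerability for up to 38 weeks. Apart from short tapers, Period 2 is the only source of information beyond Week 14, so the percentages meant to describe longer-term tolerability are the ones diluted. The tables for serious events and for events leading to discontinuation are affected in the same way.

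**Working it through.** The plan gives no sample-size calculation, projected extension entry or expected event rate, so there is no stated figure to reproduce.

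**Inputs**
- N = 20 patients dosed (approximate; SAP Section 4).
- m = number entering Period 2. Not stated, so taken as an assumption from 5 to 18. The only comparable figure in the documents is the open-label fragile X study in Protocol Section 5.3.2, where 13 of 20 enrolled patients continued. Its entry rule was different, so 13 is an illustration only.
- x = number of Period 2 patients with a given event.

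**Step 1: percentages.** The label gives x/N. The incidence among patients exposed in Period 2 is x/m. The understatement factor is (x/m)/(x/N) = N/m = 20/m, whatever the value of x.

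**Step 2: what a reader would infer from zero events.** The exact one-sided 95% upper limit is 1 − 0.05^(1/n). The plan does not produce this limit; it shows the reassurance a reader could draw from the printed denominator.

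| m entering | Factor 20/m | One patient affected: printed vs on m | Zero events, upper limit: n = 20 vs n = m |
|---|---|---|---|
| 5 | 4.00 | 5.0% vs 20.0% | 13.9% vs 45.1% |
| 10 | 2.00 | 5.0% vs 10.0% | 13.9% vs 25.9% |
| 13 | 1.54 | 5.0% vs 7.7% | 13.9% vs 20.6% |
| 15 | 1.33 | 5.0% vs 6.7% | 13.9% vs 18.1% |
| 18 | 1.11 | 5.0% vs 5.6% | 13.9% vs 15.3% |

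For example, if 10 patients enter and 4 have an event, the table prints 4/20 = 20.0% where the Period 2 incidence is 4/10 = 40.0%.

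**Step 3: which tables are affected.** Everyone dosed is exposed in Period 1 and in the study as a whole, so those denominators need no change. In Period 2 the effect is clear for patient percentages. It is less clear for sachets and treatment duration. These are continuous summaries shown with their own n, and the SAP does not say whether non-entrants are left out or scored as zero.

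**Step 4: patients dosed after Week 14 who are not in Period 2.** The Period 1 schedule footnotes (Protocol Table 5, SAP Table 4) have patients on anti-epileptic drugs who do not qualify for Period 2 taper study drug for one or two weeks after Week 14. They return at Week 16 or 17 with an adverse-event review. A Period 2 set defined only by a dose after Visit 4 would wrongly include them. Section 5.2 uses the Week 14 date as the Period 1 cutoff, so their taper events fall after Period 1 and the SAP does not say where they are counted.

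**Step 5: the Section 5.2 sentence.** Sections 6.2.4 and 8.1.1 both start the window at first dose. The Section 5.2 sentence does not parse: it names the time before treatment begins together with the end of treatment. The reference to Section 6.2.3 is to prior and concomitant medication, where starts before dosing are legitimate. The likeliest intended wording is a window between start and end of treatment.

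**The case against.** The strongest reply is that the SAP never states a percentage denominator for Period 2. The dilution is inferred from a population label, and a sensible programmer might count only entrants. Event and patient counts are tabulated and the number entering appears in disposition, so a reader could recompute the rate. This softens the consequence but leaves the defect. Section 8 is explicit that one set serves all safety analyses, nothing in the SAP points to entrants, and recomputation fails if taper events of non-entrants are in the numerator. Section 8.1.8, by contrast, does ask for the number of patients assessed in each interval of the skin diary.

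The Note to File raises a second reply: if data are no longer handled by period, the Period 2 tables may never be produced. That may be so, but the Note also leaves the SAP text standing, so their status is unclear and needs to be stated.

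Two stronger readings are tempting. A reader might infer that the primary safety percentages as a whole are wrong. They are not, because the Safety Analysis Set is right for Period 1 and for the overall tables.

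A reader might also infer from Section 5.2 that events before treatment are counted as treatment-emergent, inflating Period 1. Adverse events are collected from Screening (Protocol Section 11.2.1.1), so such records can exist. Following the sentence literally, 8 to 28 screening days against 98 treatment days would add 8/98 = 8% to 28/98 = 29% to the event count, assuming a constant event rate. But one garbled sentence stands against two clear definitions, under which the addition is 0%. That is a conflict to correct; it does not show a miscount.

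Exposure-adjusted incidence in the overall tables would be a reasonable extra, but in a descriptive study of about 20 patients with treatment duration already summarized it is a preference.

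**Conclusion.** The denominator point holds for Period 2. Followed as written, the SAP understates each Period 2 adverse-event percentage by 20/m: 2.0-fold if 10 of 20 enter, 1.5-fold if 13 of 20 enter, and between 1.1- and 4.0-fold for 18 down to 5 entrants. These sizes rest on about 20 patients dosed, on an assumed m, and on reading the population label as the percentage denominator. They apply only if the by-period tables are still produced. The documents do not support extending the point to the Period 1 or overall tables, and they do not establish that events before dosing are counted as treatment-emergent. Section 5.2 is an inconsistency that should be corrected at the same time.

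**What to change.** 1. Define a Period 2 Safety Set: patients who qualified for and entered the extension and received at least one Period 2 dose. Exclude non-qualifying patients whose only dosing after Week 14 is a taper. Use this set as the denominator for all Period 2 adverse-event, exposure and concomitant-medication summaries, and print m in the column header.
2. State how events are assigned to a period. Place taper events after Week 14 in non-continuers explicitly in Period 1 or follow-up.
3. Rewrite the Section 5.2 sentence so that a Period 1 treatment-emergent event has onset on or after first dose, and cite Section 6.2.4. Keep the medication rule separate, under Section 6.2.3.
4. State whether the by-period tables are still produced after the Note to File. Since the sponsor does not intend to update the SAP, these points could go in a further note and in table footnotes.

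The cost is wording and one population flag, with no new data. Period 2 percentages become less favourable and rest on fewer patients, so they will be less precise.

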| Pregnancy Test ^d | | | X | | | X | |
| CBD/THC PK Blood Sample | | | X | | | | |
| Blood Sample for Valproic Acid ^{e, g} | | | X | | | | |
| ABC-C | X | X | X | | | | |
| CGI-S | X | X | X | | | | |
| CGI-I | X | X | X | | | | |
| ADAMS | X | X | X | | | | |

Table 6: Period 2 Schedule of Assessments – 24-Week Extension Treatment Period, cont'd

| Study Procedures | 24-Week Treatment Period – Visit Schedule | | | Taper Period, If Applicable | | Study Visit Week 40 or Week 41 for AED Patients Tapering Study Drug ^a Visit ^a | Un-scheduled Visit(s) |
|--|---|--------------------------------------|---|--|---------------------------|--|--------------------------|
| | Visit 5 Week 22 (± 3 days) | Visit 6 Week 30 (± 3 days) | Visit 7 Week 38 EOS/ET ^a (± 3 days) | Week 39 (± 3 days) | Week 40 (± 3 days) | | |
| | Study Drug Dosing | | | Tapered 50% each week. No Study Visit | | | |
| C-SSRS | X | X | X | | | X | X |
| Qualitative Caregiver Behavioral Problems/Improvements Survey | X | X | X | | | | |
| Children’s Sleep Habit Questionnaire | | | X | | | | |
| Pediatric Anxiety Rating Scale-Revised | X | X | X | | | | |
| Daily Study Drug Application | X | X | X | X | X | | |
| Parent/caregiver Completes Daily Skin Irritation Diary ^{f, h} | X | X | X | X | X | X | X |
| Review Patient Skin Irritation Diary | X | X | X | | | X | X |
| Skin Irritation Exam ⁱ | | | X | | | X | X |
| Adverse Event Review | X | X | X | | | X | X |

Table 6 Footnotes - Period 2:

- a. Patients who withdraw prior to Period 2 Week 38 will complete the EOS/ET at Week 38. AED patients will taper study drug for 1 or 2 weeks after the EOS Visit and return on Week 40 or 41 for final discharge from the study, unless they are transitioning to receive drug through Special Access.
- b. Patients will have both weight and height taken at EOS/ET. For patients taking AEDs and returning on Week 40 or 41 to be discharged from the study, a targeted physical examination (heart, lungs, abdomen and extremities) may be performed, if the investigator deems clinically relevant.
- c. Vital signs (including blood pressure, heart rate, respiratory rate, and infrared forehead or oral or tympanic temperature) will be recorded after the patient has been sitting for at least 5 minutes. Vital signs will be assessed at each study visit pre-dose.
- d. A pregnancy test will be completed at Week 38/EOS/ET for all females of childbearing potential. Pregnancy tests can be plasma or urine.

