7.6.11. Electrocardiogram

A 12-lead resting ECG will be obtained during the Screening Visit, and at study Visits 2, 3, 4, and 7/EOS/ET Visits. As applicable, ECGs will be conducted pre-dose, within 60 minutes of study drug application. All ECGs will be reviewed by a central reader (Cardiologist). The cardiologist will interpret, sign, and date the ECGs. Clinical interpretations will be recorded in the CRF (normal or abnormal with specific abnormality noted).

Note: one ECG to be collected prior to starting treatment (Screening or Visit 2), provided that ECG is normal or has a finding that is not clinically significant.

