7.6.15. Clinical Laboratory Testing

All blood samples will be collected and handled in accordance with the instructions from the local laboratory. For collection of laboratory samples, patients should fast for approximately four to eight hours prior to having blood drawn for blood laboratory analysis. Instructions regarding the collection, processing, and shipping of these samples will be provided by the laboratory chosen for this study.

All abnormal laboratory test results will be followed to a satisfactory resolution.

Samples will be collected based on Table 4, Table 5 and Table 6 Schedule of Assessments. Routine laboratory tests (clinical chemistry, hematology, and urinalysis) will be collected at the Screening Visit, Week 6, Week 14, and Week 38 EOS/ET Visits.

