11. ASSESSMENT OF SAFETY

11.1. Safety Parameters

Patient safety will be monitored at each study visit using standard measures, including physical and neurological exams, examination of skin at application sites for irritation, vital signs (including oral, infrared forehead or tympanic temperature), 12-lead ECGs, the C-SSRS, safety laboratory tests, urinalysis, and AE monitoring.

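### Period 2 adverse-event percentages have no exposure adjustment and, as listed, a denominator that includes patients who never entered Period 2

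*SAP*

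**What the plan says.** SAP section 8 sets the by-period layout: "Study drug administration, AEs and concomitant medications will be summarized by treatment period (Period 1, 2, and overall". Section 8.1.1 repeats it for AEs: "AEs will be summarized separately for each treatment Period (1, 2) and overall (the whole study". The measure is a crude proportion with a count: "An overall summary of adverse events will include number (%) of patients reporting ≥ 1 TEAE (and number of TEAEs", and "All AE summaries will include total number of TEAEs and total number of patients with AEs". Neither section 8 nor the table list in section 11 contains a rate per patient-time. SAP 8.1 does summarise treatment duration for each period and overall.

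Period 1 lasts 14 weeks and Period 2 up to 24 (SAP 4.1). Entry to Period 2 needs at least 35% improvement in ABC-C irritability (SAP 4). Section 11 nevertheless names the Safety Analysis Set for every AE table, including the Period 2 ones, and SAP 6.4.1 defines that set as everyone who was dosed.

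On the schedule, routine laboratory tests "will be collected at the Screening Visit, Week 6, Week 14, and Week 38 EOS/ET Visits" (Protocol 7.6.15), and on-study ECGs are taken "at study Visits 2, 3, 4, and 7/EOS/ET Visits" (Protocol 7.6.11). Protocol Tables 5 and 6 place laboratory tests, ECG and physical/neurological examination at Weeks 6 and 14 and then only at Week 38. AE review continues at Weeks 22, 30 and 38. Protocol 11.1, however, says: "Patient safety will be monitored at each study visit using standard measures, including physical and neurological exams".

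The Note to File in front of the SAP, effective 16 February 2026, says that data were collected as a single arm and not by dose or by period, and that the SAP will not be updated.

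**The concern.** Safety and tolerability for up to 38 weeks is the primary objective, so these are primary-objective tables. Period 1, Period 2 and overall form matched sets (for example 14.3.2.1.1, 14.3.2.1.2 and 14.3.2.1.3), and nothing in the SAP warns the reader that the percentages have different meanings.

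A Period 2 percentage on the listed population is hard to interpret even alone. Its numerator can only come from patients who responded and continued. Its denominator includes patients who had left. Its time at risk is up to 1.7 times that of Period 1. The overall percentage has a related fault: it pools patients followed for about 14 weeks with patients followed for up to 38.

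**Working it through.** The plan states no expected AE rate, entry fraction or safety sample-size calculation, so there is no figure of its own to reproduce. The period lengths, schedule, listed population and approximate total of 20 patients come from the documents. Incidences and entry fractions below are assumptions.

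**1. Time at risk.** The length ratio is 24/14 = 1.71. Under a constant hazard, a proportion p over 14 weeks becomes 1 − (1 − p)^(24/14) over 24 weeks.
- p = 20%: 1 − 0.8^1.714 = 31.8%
- p = 30%: 1 − 0.7^1.714 = 45.7%

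**2. Denominator.** For the same affected patients, out of 20 dosed:

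| Entrants | Affected | % of entrants | % of 20 |
|---|---|---|---|
| 5 | 2 | 40 | 10 |
| 8 | 3 | 37.5 | 15 |
| 10 | 4 | 40 | 20 |
| 15 | 6 | 40 | 30 |

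**3. Both together.** With entry fraction f, full follow-up in each period and the same hazard in entrants, the Period 2 percentage of the Safety Analysis Set is f × [1 − (1 − p)^(24/14)].

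| f | Period 1 = 20% | Period 1 = 30% |
|---|---|---|
| 0.25 | 7.9% | 11.4% |
| 0.50 | 15.9% | 22.9% |
| 0.75 | 23.8% | 34.3% |
| 1.00 | 31.8% | 45.7% |

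The two effects cancel at f = p / [1 − (1 − p)^(24/14)]: 0.200/0.318 = 63% and 0.300/0.457 = 66%. Below that entry fraction Period 2 looks better than Period 1, and above it worse, although the hazard is unchanged.

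**4. What a rate does.** In the 30% example the first-event rate is −ln(0.70)/14 = 0.0255 per week, and from Period 2 entrants −ln(1 − 0.457)/24 = 0.0255 per week. Both are about 2.5 per 100 patient-weeks, so the artefact disappears.

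**5. Frequency of checks on treatment.** Laboratory tests, ECG and examination: 2/14 against 1/24 per week, a 3.4-fold fall. AE review: 2/14 against 3/24, a 1.14-fold fall (every 7 weeks against every 8). For patients who also have the Week 10 call it is 3/14 against 3/24, or 1.7-fold.

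**The case against.** The SAP presents the periods in separate tables and plans no comparison or test between them, so a time trend is something a reader would infer and not something the plan claims. Event counts and treatment duration by period are both reported, so an approximate crude event rate can be worked out by hand. The study is exploratory and descriptive, with about 20 patients. All of this is correct and limits the point. It does not supply first-event rates, which summary durations cannot give, and it does not settle the Period 2 denominator. SAP 5.2 also imputes a Week 14 cut-off for patients who stop early in Period 1, so the window for counting events may run past the end of treatment.

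A reader might go further and infer that Period 2 percentages are inflated, or that sparser testing lowers AE detection throughout Period 2. The documents do not support either. With the listed population, the first reverses unless roughly two thirds of patients enter. On the second, AE review hardly changes, vital signs and C-SSRS continue at Weeks 22 and 30, and the skin diary is daily. Protocol 11.2.1.1 generally excludes laboratory findings without clinical significance from AEs and does not count pregnancy as an AE. Laboratory, ECG and examination results are also summarised by visit, where period length plays no part. The fall in scheduled checks is a caveat on comparing periods, not a demonstrated bias.

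The Note to File might be read as having removed by-period reporting. It speaks of how data were collected and leaves the SAP unchanged, so it conflicts with SAP section 8 without resolving the matter.

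**Conclusion.** The point holds in a limited form. As written, the Period 2 AE percentages combine a longer time at risk with a denominator that includes patients who never entered, and no planned rate separates the two. Each effect can be large: 30% becomes 46% from length alone, and 40% becomes 20% from the denominator alone if half of 20 patients enter. The net direction cannot be stated, because the documents give no entry fraction.

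These sizes rest on assumed incidences, constant hazard, full follow-up, and a literal reading of the population column in SAP section 11. Selection matters as well: Period 2 consists of responders who completed Period 1, so a difference between periods could not be put down to the schedule alone, nor to a change in tolerability over time. The defect is in reporting, and it does not affect the data collected.

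**What to change.** - In SAP 8.1.1 and the Period 2 AE tables in section 11 (14.3.2.1.2, 14.3.2.2.2, 14.3.2.3.2.1, 14.3.2.3.2.2, and 14.3.2.4.2 through 14.3.2.9.2), make patients who entered Period 2 the denominator. Their number is already planned for the disposition table (SAP 6.3.1).
- Add events, and first events, per patient-time of actual exposure for Period 1, Period 2 and overall. Define the event-counting window so that it matches the exposure time, including for early stoppers covered by SAP 5.2.
- State that the period percentages are not for comparison, because Period 2 is a selected responder group, the periods differ in length, and scheduled laboratory, ECG and examination checks fall from two in 14 weeks to one in 24.
- Reconcile SAP section 8 with the Note to File on whether AEs are reported by period.
- Reconcile Protocol 11.1 and the synopsis, which describe examinations and ECGs as monitoring at every study visit, with Table 6, which shows neither at Weeks 22 and 30.

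The cost is SAP wording, about one extra column per AE table and a protocol clarification. AE onset dates and treatment duration are already collected. A separate table of test-detected AEs is not requested: the AE fields listed in Protocol 11.4 do not record how an event was found.
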